#### **4.5.4 Other risks**

##### **4.5.4.1 Pregnancy, lactation, and effects on fertility**

No preclinical reproductive studies have been conducted with tisagenlecleucel to assess whether it can cause fetal harm when administered to a pregnant woman. The human placenta forms an incomplete barrier for blood cells, allowing bidirectional passage of nucleated blood cells. Circulating maternal cells transfer to the fetus during pregnancy, where they may integrate with the fetal immune and organ systems, creating a state of maternal microchimerism (MMC) ([Loubiere et al 2006, Stevens 2016](#)). Hence, there is a potential risk that immunologically active maternal tisagenlecleucel positive T-cells may cross the placenta. Currently, the potential impact of tisagenlecleucel on the offspring's B-cells such as inducing B-cell lymphocytopenia or other potential toxicities such as effects on the development of autoimmune disease (see below) is not known.

As it is also not known whether tisagenlecleucel can cause fetal harm when administered to a pregnant woman or can affect reproduction capacity, tisagenlecleucel should not be administered to pregnant women and care should be taken to avoid conceptions.

Therefore, women of child bearing potential (WOCBP), defined as all women physiologically capable of becoming pregnant, and sexually active males are excluded from clinical trials with tisagenlecleucel unless they use adequate contraception. No data are currently available to determine the duration of contraception after receiving tisagenlecleucel. Women of child bearing potential and sexually active males must be informed that taking the study treatment may involve unknown risks to the fetus if pregnancy were to occur during the study, and agree that in order to participate in the study they must adhere to the contraception requirements outlined in the exclusion criteria. If there is any question that the subject will not reliably comply, they should not be entered or continue in the study.

There is no information regarding the presence of tisagenlecleucel in human milk, the effect on the breast-fed child or the effects of tisagenlecleucel on milk production. Nursing women are excluded from participation in this study.

## 5 Population

The target population consists of pediatric and adolescent young adult patients up to and including 25 years of age with B-cell ALL who have been previously infused once with tisagenlecleucel and have a loss of B-cell aplasia. Approximately 54 subjects will be enrolled to allow 49 subjects treated.

The investigator or designee must ensure that only subjects who meet all the following inclusion and none of the exclusion criteria at screening and prior to infusion are offered treatment in the study.

### 5.1 Inclusion criteria

Subjects eligible for inclusion in this study must meet **all** of the following criteria:

1. Must have an additional dose of unexpired, commercial tisagenlecleucel available and prescribed by a physician in the course of medical practice.
2. Signed informed consent must be obtained prior to participation in the study.
3. Age up to and including 25 years at the time of ICF signature
4. Patients must have CD-19+ Leukemia
5. Karnofsky (age  $\geq$ 16 years) or Lansky (age  $<$  16 years) performance status  $\geq$  50 at screening
6. Patients who were previously treated with commercial tisagenlecleucel and present with evidence of B-cell recovery as defined by:
  - a. Peripheral blood (PB) absolute B lymphocyte count  $\geq$  50/ $\mu$ L, **OR**
  - b. PB B lymphocyte  $\geq$  10% of the total lymphocytes
7. Subjects must meet the following hematological values without transfusion at Screening:
  - Absolute neutrophil count (ANC)  $\geq$  1,000/mm^3 ( $\geq 1\times 10^9/L$ )
  - Absolute lymphocyte count (ALC)  $>$  300/mm^3 ( $> 0.3\times 10^9/L$ )
  - Absolute number of CD3+ T cells  $>$  150/mm^3 ( $> 0.15\times 10^9/L$ )
  - Platelets  $\geq$  50 000/mm^3 ( $\geq 50\times 10^9/L$ )
  - Hemoglobin  $\geq$  8.0 g/dl ( $\geq 4.9$  mmol/L)
8. A serum creatinine of  $\leq$  1.5 times ULN or eGFR  $\geq$  60 mL/min/1.73 m^2
9. Adequate pulmonary function defined as:
  - No or mild dyspnea ( $\leq$  Grade 1)
  - Oxygen saturation measured by pulse oximetry  $>$  90% on room air
10. Liver function tests including the following:
  - ALT or AST  $\leq$  5 times the ULN
  - Total bilirubin  $<$  2mg/dl (with the exception of subjects with Gilbert's syndrome. Subjects with Gilbert's syndrome may be included if their total bilirubin is  $<$  4mg/dl).

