### 5.2 Exclusion criteria

Subjects eligible for this study must not meet **any** of the following criteria:

1. Prior gene therapy other than tisagenlecleucel

2. Prior adoptive T cell therapy other than tisagenlecleucel
3. Active CNS involvement by malignancy
4. Systemic chemotherapy or radiotherapy within 2 weeks prior to enrolment or tyrosine kinase inhibitors (for patients with Philadelphia chromosome positive ALL) within 1 week prior to enrolment.

Notes:

- Non-hematologic toxicity from prior treatment must be resolved to CTCAE grade 1 or better.
- The use of hydroxyurea is permitted for temporary control of WBC elevations in patients with aggressive disease both prior and during the first 7 days after enrolment.
- The use of corticosteroids within one week prior to enrolment is also allowed

5. Presence of active or prior hepatitis B or C as indicated by serology (for detailed criteria see [Table 16-2](#)). Serology must be repeated, if the interval between testing at Screening and tisagenlecleucel infusion exceeds 8 weeks.
6. HIV positivity as indicated by serology. Serology must be repeated, if the interval between testing at screening and tisagenlecleucel infusion exceeds 8 weeks.
7. Clinically significant acute infection confirmed by clinical evidence, imaging, or positive laboratory tests within 72 hrs prior to tisagenlecleucel infusion (e.g., blood cultures, PCR for DNA/RNA, etc.).
8. Previous or concurrent malignancy except for curatively treated non-melanoma skin cancers, in situ carcinoma (e.g. cervix, breast, bladder, prostate), and cancers in complete remission for at least 3 years and without evidence of recurrence.
9. Pregnant or nursing (lactating) women. NOTE: Women of child-bearing potential must have a negative serum pregnancy test performed within 24 hours before lymphodepletion (if performed) and prior to tisagenlecleucel infusion.
10. Women of child-bearing potential, defined as all women physiologically capable of becoming pregnant, **unless** they agree to use highly effective methods of contraception from enrollment into this study through at least 12 months after the tisagenlecleucel infusion and until CAR T-cells are no longer present by qPCR on two consecutive tests. qPCR test results will be available upon request. Highly effective contraception methods include:

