### **6.1.2 Pre-infusion evaluation**

If any of the following criteria is met tisagenlecleucel infusion must be delayed until resolution to grade 1. If the period of delay is more than 4 weeks from completing lymphodepletion and there is no significant cytopenia (see [Section 6.1.6](#)) Lymphodepletion should be repeated, and these criteria will need to be re-checked prior to tisagenlecleucel infusion.

1. Rapidly progressing primary disease (e.g. leukemia/lymphoma)
2. Clinical evidence of CNS involvement by primary disease
3. Laboratory abnormalities that, in the opinion of the investigator, may impact subject safety or the subjects' ability to receive tisagenlecleucel.
4. Following clinical abnormalities:
  - Pulmonary: Requirement for supplemental oxygen to keep saturation greater than 90% or presence of progressive radiographic abnormalities on chest x-ray
  - Cardiac arrhythmia not controlled with medical management
  - Hypotension requiring vasopressor support
  - Clinically significant active infection confirmed by clinical evidence, imaging, or positive laboratory tests (e.g., blood cultures, PCR for DNA/RNA, etc.). NOTE: All viral serology must be repeated, if the interval between testing prior to lymphodepletion and tisagenlecleucel infusion exceeds 8 weeks.
5. A significant change in clinical status that would, in the opinion of the investigator, increase the risk of adverse events associated with tisagenlecleucel
6. Toxicities from chemotherapy (including lymphodepletion).
7. Prohibited medications as described in [section 6.2.1](#)

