## 10.2 Additional Safety Monitoring

### 10.2.1 Liver safety monitoring

To ensure subject safety and enhance reliability in determining the hepatotoxic potential of tisagenlecleucel, a standardized process for identification, monitoring and evaluation of liver events has to be followed.

The following two categories of abnormalities / adverse events have to be considered during the course of the study (irrespective of whether classified/reported as AE/SAE):

- Liver laboratory triggers, which will require repeated assessments of the abnormal laboratory parameter
- Liver events, which will require close observation, follow-up monitoring and contributing factors are recorded on the appropriate CRFs

Please refer to [Table 16-4](#) in Appendix 3 for complete definitions of liver laboratory triggers and liver events.

Every liver event defined in [Table 16-3](#) should be followed up by the investigator or designated personnel at the trial site, as summarized below. Additional details on actions required in case of liver events are outlined in [Table 16-4](#). Repeat liver chemistry tests (ALT, AST, TBL, PT/INR, ALP and G-GT) to confirm elevation.

These liver chemistry repeats should be performed using the local laboratory used by the site. Repeated laboratory test results must be reported as appropriate.

If the initial elevation is confirmed, close observation of the subject will be initiated, including consideration of treatment interruption if deemed appropriate.

- Discontinuation of tisagenlecleucel, if appropriate
- Hospitalization of the subject if appropriate
- Causality assessment of the liver event
- Thorough follow-up of the liver event, which can include based on investigator's discretion:
  - Serology tests, imaging (e.g., such as abdominal US, CT or MRI, as appropriate) and pathology assessments, gastroenterologist's or hepatologist's consultancy; obtaining more detailed history of symptoms and prior or concurrent diseases, history of concomitant drug use, exclusion of underlying liver disease, obtaining a history of exposure to environmental chemical agents.

All follow-up information, and the procedures performed must be recorded as appropriate in the CRF.

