## **11.3 Site monitoring**

Before study initiation, at a site initiation visit or at an investigator's meeting, a Novartis representative or delegated CRO representative will review the protocol and data capture requirements (i.e. eSource DDE or eCRFs) with the investigators and their staff. During the study, Novartis employs several methods of ensuring protocol and GCP compliance and the quality/integrity of the sites' data. The field monitor will visit the site to check the completeness of subject records, the accuracy of data capture / data entry, the adherence to the protocol and to Good Clinical Practice, the progress of enrollment, and to ensure that study treatment is being stored, dispensed, and accounted for according to specifications. Key study personnel must be available to assist the field monitor during these visits. Continuous remote monitoring of each site's data may be performed by a centralized delegated CRO organization. Additionally, a central analytics organization may analyze data & identify risks & trends for site operational parameters, and provide reports to Novartis clinical teams to assist with trial oversight.

The investigator must maintain source documents for each subject in the study, consisting of case and visit notes (hospital or clinic medical records) containing demographic and medical information, laboratory data, electrocardiograms, and the results of any other tests or assessments. All information on CRFs must be traceable to these source documents in the subject's file. Data not requiring a separate written record will be defined before study start and will be recorded directly on the CRFs. The investigator must also keep the original informed consent form signed by the subject (a signed copy is given to the subject).

The investigator must give the monitor access to all relevant source documents to confirm their consistency with the data capture and/or data entry. Novartis monitoring standards require full verification for the presence of informed consent, adherence to the inclusion/exclusion criteria,

documentation of SAEs, and of data that will be used for all primary variables. Additional checks of the consistency of the source data with the CRFs are performed according to the study-specific monitoring plan. No information in source documents about the identity of the subjects will be disclosed.

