## Appendix 3: Liver event and Laboratory trigger Definitions and Follow-up Requirements

**Table 16-3 Liver Event and Laboratory Trigger Definitions**

		Definition/ threshold
LIVER LABORATORY TRIGGERS		3 x ULN ALT / AST $\leq$ 5 x ULN · 1.5 x ULN $<$ TBIL $\leq$ 2 x ULN
LIVER EVENTS		ALT or AST $>$ 5 x ULN ALP $>$ 2 x ULN (in the absence of known bone pathology) TBIL $>$ 2 x ULN (in the absence of known Gilbert syndrome) ALT or AST $>$ 3 x ULN and INR $>$ 1.5 Potential Hy's Law cases (defined as ALT or AST $>$ 3 x ULN and TBIL $>$ 2 x ULN [mainly conjugated fraction] without notable increase in ALP to $>$ 2 x ULN) Any clinical event of jaundice (or equivalent term) ALT or AST $>$ 3 x ULN accompanied by (general) malaise, fatigue, abdominal pain, nausea, or vomiting, or rash with eosinophilia Any adverse event potentially indicative of a liver toxicity*

\*These events cover the following: hepatic failure, fibrosis and cirrhosis, and other liver damage-related conditions; the non-infectious hepatitis; the benign, malignant and unspecified liver neoplasms TBIL: total bilirubin; ULN: upper limit of normal

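### As worded, inclusion 10 is met when only one of ALT and AST is within 5 x ULN, leaving the other with no numeric ceiling at entry (minor wording correction)

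*Protocol*

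**What the plan says.** Protocol Section 5.1 requires every numbered inclusion criterion to be met. Criterion 10 has two liver bullets. The first is "ALT or AST $\leq$ 5 times the ULN". The second is a separate total bilirubin limit: below 2 mg/dl, or below 4 mg/dl with Gilbert's syndrome. Section 5 applies the criteria both at screening and before infusion.

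Four other places bear on raised transaminases:

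- **Section 5.2, note to exclusion 4:** "Non-hematologic toxicity from prior treatment must be resolved to CTCAE grade 1 or better".
- **Section 6.1.2:** if a listed condition is present, "tisagenlecleucel infusion must be delayed until resolution to grade 1". Item 3 covers laboratory abnormalities that the investigator considers relevant. Item 5 covers a significant change in clinical status, again by investigator judgement. Item 6 covers toxicity from chemotherapy, including lymphodepletion, with no judgement clause.
- **Section 6.5.1.1:** allows delay when the patient's condition or laboratory values have changed relative to the eligibility criteria, as judged by the treating physician.
- **Table 16-3 (Appendix 3):** lists "ALT or AST $>$ 5 x ULN" as a liver event.

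The SAP does not discuss the criterion.

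**The concern.** A limit of the at-or-below kind that joins two measurements with *or* is satisfied by either one. Requiring all criteria to be met joins the numbered items to each other; it does not turn the *or* inside item 10 into *and*. The rest of the list does not settle the meaning. Criterion 6 (B-cell count or percentage) and criterion 8 ("1.5 times ULN or eGFR") use the word as a free alternative. Criterion 5 ("16 years) or Lansky (age") uses it to mean whichever scale applies at the patient's age.

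This is the only numeric ALT/AST limit for entry. Section 11.3 says that the sponsor's monitoring standards "require full verification for the presence of informed consent, adherence to the inclusion/exclusion criteria", so the printed sentence is what compliance is checked against. A patient could enter with one enzyme well above the level that the protocol treats as a liver event once on study. Transaminitis is a listed sign of CRS (Table 4-1) and enters its grading (Table 4-2), so a high entry value would also make later liver findings harder to attribute.

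**Working it through.** The plan gives no figure to reproduce here; the check is one of logic.

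**Rules compared** (values in multiples of ULN):

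- A, as printed in inclusion 10: ALT <= 5 or AST <= 5.
- B, the probable intent: ALT <= 5 and AST <= 5.
- C, the Table 16-3 line: ALT > 5 or AST > 5.

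| ALT | AST | A | B | C |
|---|---|---|---|---|
| 4 | 4 | met | met | no event |
| 4 | 9 | met | not met | event |
| 9 | 4 | met | not met | event |
| 4 | 20 | met | not met | event |
| 9 | 9 | not met | not met | event |

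A and B differ exactly when one enzyme is at or below 5 and the other is above it. The 4 and 20 row shows that A sets no ceiling on the second enzyme.

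**Evidence of intent.** With a greater-than sign, *or* is the right word: C flags the patient if either enzyme is high. The negation of C is B, not A. The same pairing and threshold, carried over to an at-or-below limit, therefore needs *and*.

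**Do other rules stop the 4 and 9 patient?**

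- Bilirubin limit: it does not cap ALT or AST.
- Exclusion 4 note: yes, if the elevation is toxicity from prior treatment; otherwise no.
- Exclusion 5: yes, if the cause is hepatitis B or C that fails the serology rules; otherwise no.
- Section 6.1.2, items 3 and 5: only on investigator judgement, with no number. They delay infusion and do not bar enrollment.
- Section 6.1.2, item 6: mandatory, but only for chemotherapy toxicity, and again a delay to infusion.
- Section 6.5.1.1: physician judgement, measured against the eligibility criteria, so it inherits the wording of item 10.

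What is left is a patient whose elevation has some other cause, whose bilirubin is within its limit and who meets every other criterion.

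**Reach of the correction.** Table 16-3 has 8 liver-event lines. Rule B makes one of them (either enzyme above 5) impossible at entry. The other 7 are not addressed; for example, ALT 4 x ULN with INR above 1.5 could still be present. This counts table lines and does not measure risk.

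**The case against.** The strongest reply is that this is a slip that clinicians will read correctly. Under a heading about liver function tests, the ordinary reading is that both enzymes must be within the limit, and Table 16-3 supports it. The sponsor's medical staff are available for questions (Section 10.1.1). This largely stands: intent can be recovered, so the point is minor. It does not make the sentence right, because criteria 6 and 8 use the same word permissively.

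The safeguards also narrow the gap. Every patient has already had tisagenlecleucel, so prior-treatment toxicity is an obvious cause to consider, and the exclusion 4 note then applies. Item 6 of Section 6.1.2 adds a mandatory delay for chemotherapy toxicity. That stands, but neither covers every cause.

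The interpretability argument is modest. Table 4-2 counts grade 4 transaminitis only towards CRS grade 3, and a raised baseline value would be visible in the data.

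A reader might go further in three ways that the documents do not support:

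- *Monitors would pass such patients, or sites would diverge.* Section 11.3 says adherence is verified; it does not say how an ambiguous criterion is read.
- *Any patient with AST 9 x ULN could enter without a deviation.* The exclusion 4 note makes that false when prior treatment is the cause.
- *The entry rule contradicts Appendix 3.* Section 10.2.1 introduces that scheme with "The following two categories of abnormalities / adverse events have to be considered during the course of the study". It is a follow-up scheme, not an entry rule.

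**Conclusion.** The criterion is mis-worded. As printed it caps only one of the two enzymes, and no other entry criterion supplies a numeric cap on the second. The practical size is small. It concerns patients with one enzyme above 5 x ULN and the other at or below it, bilirubin within its limit, and a cause other than prior treatment. Their number cannot be estimated from the documents.

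This is a minor eligibility and safety correction. It does not bear on the primary endpoint (a B-cell measure), the sample size or the analysis. Nor does it govern who receives the commercial product outside the study (Section 6.1).

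SAP Sections 2.6 and 4 record closure for low enrollment after 5 of 54 planned patients, for reasons unrelated to safety, so a change now has little prospective effect in this trial. The conclusion assumes the literal reading of *or*; that neither enzyme should exceed 5 x ULN is an inference about intent, drawn mainly from Table 16-3.

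**What to change.** Reword the first bullet of inclusion 10 so that ALT and AST must each be at or below 5 times the ULN. Leave the threshold, the bilirubin limit and Appendix 3 as they are.

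No extra test is needed: both enzymes are in the chemistry panel (Table 8-4), which is scheduled at Screening and D1 (Table 8-1). The edit is a word or two, but in a running trial Section 14.1 would require a written amendment with sponsor and IRB/IEC approval, and health authority approval where required.

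For this closed trial, check both screening enzymes, as multiples of ULN, for the 5 enrolled patients in the laboratory listing planned for the Enrolled Set (SAP Section 2.9.2). A low/normal/high flag alone would not separate 4 from 9 x ULN. Correct the sentence before it is reused in another protocol.

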### 5.2 Exclusion criteria

Subjects eligible for this study must not meet **any** of the following criteria:

1. Prior gene therapy other than tisagenlecleucel

2. Prior adoptive T cell therapy other than tisagenlecleucel
3. Active CNS involvement by malignancy
4. Systemic chemotherapy or radiotherapy within 2 weeks prior to enrolment or tyrosine kinase inhibitors (for patients with Philadelphia chromosome positive ALL) within 1 week prior to enrolment.

Notes:

- Non-hematologic toxicity from prior treatment must be resolved to CTCAE grade 1 or better.
- The use of hydroxyurea is permitted for temporary control of WBC elevations in patients with aggressive disease both prior and during the first 7 days after enrolment.
- The use of corticosteroids within one week prior to enrolment is also allowed

5. Presence of active or prior hepatitis B or C as indicated by serology (for detailed criteria see [Table 16-2](#)). Serology must be repeated, if the interval between testing at Screening and tisagenlecleucel infusion exceeds 8 weeks.
6. HIV positivity as indicated by serology. Serology must be repeated, if the interval between testing at screening and tisagenlecleucel infusion exceeds 8 weeks.
7. Clinically significant acute infection confirmed by clinical evidence, imaging, or positive laboratory tests within 72 hrs prior to tisagenlecleucel infusion (e.g., blood cultures, PCR for DNA/RNA, etc.).
8. Previous or concurrent malignancy except for curatively treated non-melanoma skin cancers, in situ carcinoma (e.g. cervix, breast, bladder, prostate), and cancers in complete remission for at least 3 years and without evidence of recurrence.
9. Pregnant or nursing (lactating) women. NOTE: Women of child-bearing potential must have a negative serum pregnancy test performed within 24 hours before lymphodepletion (if performed) and prior to tisagenlecleucel infusion.
10. Women of child-bearing potential, defined as all women physiologically capable of becoming pregnant, **unless** they agree to use highly effective methods of contraception from enrollment into this study through at least 12 months after the tisagenlecleucel infusion and until CAR T-cells are no longer present by qPCR on two consecutive tests. qPCR test results will be available upon request. Highly effective contraception methods include:
  - Total abstinence (when this is in line with the preferred and usual lifestyle of the subject). Periodic abstinence (e.g., calendar, ovulation, symptothermal, post-ovulation methods) and withdrawal are not acceptable methods of contraception
  - Female sterilization (have had surgical bilateral oophorectomy with or without hysterectomy), total hysterectomy, or tubal ligation at least six weeks before taking study treatment. In case of oophorectomy alone, only when the reproductive status of the woman has been confirmed by follow up hormone level assessment
  - Male sterilization (at least 6 months prior to screening). For female subjects on the study, the vasectomized male partner should be the sole partner for that subject

- Use of oral, (estrogen and progesterone), injected or implanted hormonal methods of contraception or placement of an intrauterine device (IUD) or intrauterine system (IUS), or other forms of hormonal contraception that have comparable efficacy (failure rate <1%), for example hormone vaginal ring or transdermal hormone contraception. In case of use of oral contraception women should have been stable on the same pill for a minimum of 3 months before enrollment into this study.

Women are considered post-menopausal and not of child bearing potential if they have had 12 months of natural (spontaneous) amenorrhea with an appropriate clinical profile (e.g. age appropriate history of vasomotor symptoms) or have had surgical bilateral oophorectomy (with or without hysterectomy), total hysterectomy or bilateral tubal ligation at least six weeks ago. In the case of oophorectomy alone, only when the reproductive status of the woman has been confirmed by follow up hormone level assessment is she considered not of child bearing potential.

**NOTE:** If local regulations deviate from the contraception methods listed above to prevent pregnancy, local regulations apply and will be described in the ICF.

11. Sexually active males must use a condom during intercourse from enrollment into this study through at least 12 months after the tisagenlecleucel infusion and until CAR T-cells are no longer present by qPCR on two consecutive tests. qPCR test results will be available upon request. A condom is required for all sexually active male participants to prevent them from fathering a child AND to prevent delivery of study treatment via seminal fluid to their partner.
12. Known hypersensitivity to the excipients of tisagenlecleucel or to any product to be given to the patient as per the study protocol (e.g. tocilizumab and lymphodepleting agents)
13. Any study procedure (e.g., lumbar puncture) that, in the investigator's judgment and/or according to clinical standards, is a contraindication to participation in the study.
14. Cardiac disorders including
  - Unstable angina and/or myocardial infarction within 6 months prior to screening
  - History of myocardial infarction (MI), unstable angina pectoris, or coronary artery bypass graft (CABG) within 6 months prior to screening
  - Clinically significant cardiac arrhythmias (e.g., ventricular tachycardia), complete left bundle branch block, high-grade AV block (e.g., bifascicular block, Mobitz type II and third degree AV block)
  - LVEF <45% as determined by ECHO or MRA or MUGA
  - NYHA functional class III or IV ([Chavey et al 2001](#))
15. Subjects enrolled in this study are not permitted to participate in additional parallel investigational drug or device studies

